7.2 Exclusion criteria

Patients should not enter the study if any of the following exclusion criteria are fulfilled:

- 1. Participation in another clinical study with an investigational product during the last 30 days.
- 2. Concurrent enrolment in another clinical study, unless it is an observational (non-interventional) clinical study or during the follow-up period of an interventional study.
- 3. Previous chemo- or radiotherapy for SCLC. Patients who have undergone surgery, but no adjuvant therapy are eligible.
- 4. Any unresolved toxicity NCI CTCAE Grade ≥2 from previous anticancer therapy with the exception of alopecia, vitiligo, and the laboratory values defined in the inclusion criteria.
- 5. Patients with Grade ≥2 neuropathy will be evaluated on a case-by-case basis after consultation with the Chief Investigator.

- 6. Patients with irreversible toxicity not reasonably expected to be exacerbated by treatment with durvalumab may be included only after consultation with the Chief Investigator.
- 7. Any concurrent chemotherapy, investigational product or biologic cancer therapy.
- 8. Any prior checkpoint inhibitor therapy, including durvalumab.
- 9. Radiotherapy treatment to more than 30% of the bone marrow or with a wide field of radiation within 4 weeks of the first dose of study drugs.
- 10. Immediate need for thoracic radiotherapy or bulky disease outside the thorax, or need for such radiotherapy before completion of chemo-immunotherapy
- 11. Major surgical procedure within 28 days prior to the first dose of study drugs. Note: Local surgery of isolated lesions for palliative intent is acceptable.
- 12. History of allogenic organ transplantation.
- 13. Active or prior documented autoimmune or inflammatory disorders (including inflammatory bowel disease [e.g., colitis or Crohn's disease], diverticulitis [with the exception of diverticulosis], systemic lupus erythematosus, Sarcoidosis syndrome, or Wegener syndrome [granulomatosis with polyangiitis, Graves' disease, rheumatoid arthritis, hypophysitis, uveitis, etc]). The following are exceptions to this criterion:
 - a. Patients with vitiligo or alopecia.
 - b. Patients with hypothyroidism (e.g., following Hashimoto syndrome) stable on hormone replacement.
 - c. Any chronic skin condition that does not require systemic therapy.
 - d. Patients without active disease in the last 5 years may be included but only after consultation with the Chief Investigator.
 - e. Patients with celiac disease controlled by diet alone.
- 13. Uncontrolled intercurrent illness, including but not limited to, ongoing or active infection, symptomatic congestive heart failure, uncontrolled hypertension, unstable angina pectoris, cardiac arrhythmia QTcF value >470 ms on ECG, interstitial lung disease, serious chronic gastrointestinal conditions associated with diarrhea, or psychiatric illness/social situations that would limit compliance with study requirement, substantially increase risk of incurring AEs or compromise the ability of the patient to give written informed consent.
- 14. History of another primary malignancy except for:
 - Malignancy treated with curative intent and with no known active disease ≥5 years before the first dose of IP and of low potential risk for recurrence.
 - Localized breast or prostate cancer treated with hormonal therapy alone.
 - Adequately treated non-melanoma skin cancer or lentigo maligna without evidence of disease
 - Adequately treated carcinoma in situ without evidence of disease.
- 15. Leptomeningeal carcinomatosis.
- 16. Untreated, symptomatic central nervous system (CNS) metastases. Any neurologic symptoms that developed either as a result of the brain metastases or their treatment must have resolved or be stable either, without the use of steroids, or are stable on steroids and/or anticonvulsants prior to the start of treatment.
- 17. History of active primary immunodeficiency.
- 18. Active infection including tuberculosis (clinical evaluation that includes clinical history, physical examination and radiographic findings, and TB testing in line with local practice), hepatitis B (known positive HBV surface antigen (HBsAg) result), hepatitis C. Patients with a past or resolved HBV infection (defined as the presence of hepatitis B core antibody [anti-HBc] and absence of HBsAg) are eligible. Patients positive for hepatitis C (HCV) antibody are eligible only if polymerase chain reaction is negative for HCV RNA.
- 19. Current or prior use of immunosuppressive medication within 14 days before the first dose of durvalumab. The following are exceptions to this criterion:

Study Number T Protocol Version Number 1

TRIPLEX 1.1 05-IAN-2022

- Intranasal, inhaled, topical steroids, or local steroid injections (e.g., intra articular injection).
- Systemic corticosteroids at physiologic doses not to exceed 10 mg/day of prednisone or its equivalent.
- Steroids as premedication for hypersensitivity reactions (e.g., CT scan premedication).
- 20. Receipt of live attenuated vaccine within 30 days prior to the first dose of IP. Note: Patients, if enrolled, should not receive live vaccine whilst receiving IP and up to 30 days after the last dose of IP.
- 21. Female patients who are pregnant or breastfeeding or male or female patients of reproductive potential who are not willing to employ effective birth control from screening to 90 days after the last dose of durvalumab monotherapy.
- 22. Known allergy or hypersensitivity to any of the study drugs or any of the study drug excipients.
- 23. Judgment by the investigator that the patient is unsuitable to participate in the study and the patient is unlikely to comply with study procedures, restrictions and requirements.

Procedures for withdrawal of incorrectly enrolled patients are presented in 9.1.2.

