^hFor women of childbearing potential only. A urine or serum pregnancy test is acceptable. Women of childbearing potential are required to have a pregnancy test within 7 days prior to the first dose of study drugs and then before every durvalumab course. Pregnancy test may occur on Day 1, but results must be available and reviewed by the treating physician or Investigator prior to commencing an infusion.

Hepatitis B surface antigene (HBsAg), Hepatitis B core antibody (HBcAb), and Hepatitis C antibody (HCV Ab) tests are mandatory. If a patient has a negative HBsAg test and a positive HBcAb test, an HBV DNA test must be performed to determine if the patient has an HBV infection. If a patient has a positive HCV Ab test, an HCV RNA test must be performed to determine if the patient has an HCV infection.

FEV1, FEV1%, FVC, FVC%, and DLCO%

kRECIST assessments will be performed on images from CT of the chest and upper abdomen and MRI of the brain, each preferably with IV contrast. Additional anatomy should be imaged based on signs and symptoms of individual patients at baseline and follow-up. Confirmation of response is not mandatory. If an unscheduled assessment was performed and the patient has not progressed, every attempt should be made to perform the subsequent assessments at their next scheduled visit.

CT scan for radiotherapy planning may be used for patients in the experimental arm. A regular CT scan should be performed for patients in the control arm at the same time as CT scans for radiotherapy planning would be performed, usually 3-4 weeks after the first day of the first chemo-immunotherapy course.

^mMay be replaced with CT if MRI is unavailable.

ⁿArchival diagnostic material or re-biopsy for confirmation of suspected relapse.

^oNot mandatory.

Year	1				2					
Week	21	29	37	45	1	9	17	25	33	41
Durvalumab	D	urvalumab every	4 weeks until pr	ogressive diseas	e and need for o	ther treatment,	unacceptable to	kicity or patients	wish to disconti	nue
Clinical examination/ performance status/weight	х	х	х	х	Х	х	х	Х	Х	х
Concomitant medication	Х	Х	Х	Х	Х	X	X	Х	X	Х
HRQoL (QLQ C30 + LC13)	Х	X	X	Х	X		X		X	
Cognitive function (MoCA)	Х				Х					Х
Clinical chemistry ^e	Х	Х	Х	Х	Х	Х	Х	Х	Х	Х
Hematology	Х	Х	Х	Х	Х	X	X	Х	Х	Х
Pregnancy test in women of childbearing potential ^h					Before every du	urvalumab course	2			
Assessment of adverse events	Х	Х	Х	Х	Х	X	X	Х	X	Х
CT thorax/upper abdomenk	Х	Х	Х	Х	Х	Х	Х	Х	Х	Х
MRI of the brain ^{k,m}	(X)°	Х	(X)°	Х	(X)°	Х	(X)°	Х	(X)°	Х

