- The patient does not have any significant, unacceptable, or irreversible toxicities that indicate continuing treatment will not further benefit the patient. The patient may not have experienced a toxicity that required permanent discontinuation of study treatment.
- There is absence of clinical symptoms or signs indicating clinically significant disease progression accompanied by a decline in WHO/ECOG performance status to >1
- There is absence of rapid disease progression or threat to vital organs or critical anatomical sites (e.g. CNS-metastasis, respiratory failure due to tumor compression, or spinal cord compression) requiring urgent alternative medical intervention
- The patient still fulfills the eligibility criteria for this study (see 7.1) with the exception of inclusion criteria 8, 9, 11 and 12 and exclusion criteria 3 and 8. Patients must agree to restart durvalumab therapy.
- The patient has not received an intervening systemic anticancer therapy after their assigned treatment discontinuation.
- The patient has had a retreatment baseline tumor assessment within a maximum of 28 days
 prior to restarting their assigned treatment; all further scans should occur with the same
 frequency as during the initial 12 months of treatment (relative to the date of restarting
 treatment) until study treatment is stopped (maximum of 12 months of further treatment).

Patients who the Investigator determine may not continue treatment after RECIST 1.1-defined PD will be followed for survival. Patients who have discontinued treatment due to toxicity or symptomatic deterioration, or who have commenced subsequent anticancer therapy, will be followed up with tumor assessments until RECIST 1.1-defined PD plus an additional follow-up scan or until death (whichever comes first) and followed for survival.

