9.1.2 Procedures for handling patients incorrectly enrolled

Patients who are incorrectly enrolled and/or randomized will be discussed with the Chief Investigator before deciding whether the patient should be withdrawn. If there has been a major protocol violation, the patient will be withdrawn from the study.

10. Restrictions during the study and concomitant treatment(s)

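### The schedule orders an HBV DNA test in HBsAg-negative, anti-HBc-positive patients, but exclusion criterion 18 makes them eligible whatever the result

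*Protocol*

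**What the plan says.** The hepatitis footnote to the schedule of assessments (Protocol, section 2) makes HBsAg, anti-HBc and HCV antibody tests mandatory. It then adds a reflex test for patients who lack the surface antigen but carry the core antibody; for them, "an HBV DNA test must be performed to determine if the patient has an HBV infection". A parallel sentence orders HCV RNA in HCV antibody-positive patients.

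Exclusion criterion 18 in section 7.2 (no. 19 in the synopsis, with the same wording on this point) opens with "Active infection including tuberculosis" and goes on to list hepatitis B, which it ties in parentheses to a known positive HBsAg result. It then says: "Patients with a past or resolved HBV infection (defined as the presence of hepatitis B core antibody [anti-HBc] and absence of HBsAg) are eligible". The next sentence deals with hepatitis C: "Patients positive for hepatitis C (HCV) antibody are eligible only if polymerase chain reaction is negative for HCV RNA".

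A separate criterion in section 7.2, on uncontrolled intercurrent illness, also names "ongoing or active infection".

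**The concern.** The footnote treats the HBsAg-negative, anti-HBc-positive pattern as undecided until HBV DNA is known. The criterion treats the same pattern as decided: past or resolved, therefore eligible. A mandatory test is ordered and its result has no stated consequence.

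Three things depend on which reading a site takes.

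- **Exposure.** Read literally, criterion 18 does not keep out a patient whom the protocol's own test has shown to have an HBV infection. That patient would receive carboplatin/etoposide plus durvalumab, for which hepatitis and transaminase increases are listed adverse events of special interest (section 13.4.3).
- **Status after randomization.** Section 9.1.2 says: "Patients who are incorrectly enrolled and/or randomized will be discussed with the Chief Investigator before deciding whether the patient should be withdrawn". Whether a DNA-positive patient belongs in that group depends on the reading. The intention-to-treat set in section 14.2.2 is also limited to eligible randomized patients.
- **Later use of the criteria.** Section 8.2.6 requires patients treated through progression or restarting durvalumab still to meet the eligibility criteria, "with the exception of inclusion criteria 8, 9, 11 and 12 and exclusion criteria 3 and 8". Exclusion criterion 18 is not among those exceptions.

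**Working it through.** No arithmetic applies beyond a count, so the check compares the texts.

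**1. Same patients.** The footnote triggers HBV DNA testing when HBsAg is negative and anti-HBc is positive. Criterion 18 defines past or resolved infection as anti-HBc present and HBsAg absent. These are the same group.

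**2. Where each confirmatory test is named in the protocol.**

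| Test | Schedule footnote | Synopsis no. 19 | Section 7.2 no. 18 | Total |
|---|---|---|---|---|
| HBV DNA | 1 | 0 | 0 | 1 |
| HCV RNA | 1 | 1 | 1 | 3 |

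The footnote treats the two viruses in parallel. The criterion completes the rule only for hepatitis C.

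**3. Outcome by HBV DNA result (HBsAg negative, anti-HBc positive).**

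| HBV DNA | Under the hepatitis B sentence | Under the active-infection wording |
|---|---|---|
| Negative | Eligible | Eligible |
| Positive | Eligible | Can be excluded |

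The readings differ for 1 of the 2 possible results.

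**4. Does other text settle the DNA-positive case?**

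- Within criterion 18, hepatitis B is tied to a positive HBsAg, which this patient does not have, and the specific eligibility sentence follows.
- The intercurrent-illness criterion can support exclusion, but it concerns uncontrolled illness. Applying it to an asymptomatic DNA-positive patient takes judgement.
- Section 13.1 names HBsAg, HCV antibody and HIV antibody at screening. It names neither anti-HBc nor HBV DNA, although its list need not be exhaustive.
- The ALT and bilirubin limits at entry (section 7.1), chemistry at each chemo-immunotherapy course (section 2) and dose interruption for an unexplained potential Hy's Law case (section 13.15.2) limit harm. None of them decides eligibility.

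The protocol therefore supports both answers for a DNA-positive patient and gives no rule for choosing between them.

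**The case against.** The best defence reads the two texts together. Serology identifies the candidate and DNA shows whether infection is still present, so a DNA-positive patient is not truly past or resolved and falls under active infection. Section 7.2 also bars entry if any one exclusion applies, so an eligibility sentence inside one criterion waives only that criterion, and the intercurrent-illness criterion remains available. On this view the intended answer is easy to infer and only a cross-reference is missing.

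Part of this stands. Exclusion is probably what was meant, since it gives the test its stated purpose, and a site may reach that result through the other criterion. But the parenthesis defines past or resolved by serology alone, so the combined reading has to set aside the criterion's own definition. The fallback criterion depends on individual judgement.

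Other limits also stand. Divergence between sites is inferred from the wording; nothing in the protocol shows that it is likely. Hepatitis tests are scheduled only at screening, so section 8.2.6 will seldom raise a new question. Disputed enrolments go to one Chief Investigator, which centralises the decision once a case is raised but does not state the rule beforehand.

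**Conclusion.** The concern holds. The schedule and the exclusion criterion contradict each other on whether HBsAg-negative, anti-HBc-positive patients need a negative HBV DNA result, and the literal eligibility sentence covers patients whom the mandatory test shows to be infected.

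The reach is small. Only DNA-positive patients are affected. The protocol gives no prevalence and none is assumed here; the number may be zero of the approximately 302 planned patients. The primary endpoint, alpha and power are not affected. The correction should still be made, because the point concerns patient safety and uniform eligibility, and eligibility rules belong in the protocol rather than in an analysis plan. The conclusion rests only on the wording of the sections cited.

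**What to change.** In section 7.2 no. 18 and synopsis no. 19, state that HBsAg-negative, anti-HBc-positive patients are eligible only if HBV DNA is negative, in the same form as the hepatitis C sentence that follows. If the sponsor does intend to enrol DNA-positive patients, the criterion should say so explicitly. For consistency, anti-HBc and the reflex HBV DNA test could also be named in section 13.1.

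The essential change is one clause in two places. It adds no test, because the schedule already requires HBV DNA. The downside is that an occasional patient becomes ineligible.

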7.3 Withdrawal of patients from study treatment and/or study

7.3.1 Permanent discontinuation of chemotherapy and durvalumab

Discontinuation of study treatment, for any reason, does not impact the patient's participation in the study. A patient who decides to discontinue IP should be asked about the reason(s) for discontinuation and the presence of any AE. The patient should continue attending subsequent study visits, and data collection should continue according to the study protocol. If the patient does not agree to continue in-person study visits, a modified follow-up must be arranged to ensure the collection of endpoints and safety information. This follow-up could be a telephone contact with the patient, a contact with a relative or treating physician, or information from medical records. The approach taken should be recorded in the medical records. A patient who agrees to modified follow-up is not considered to have withdrawn consent or to have withdrawn from the study.

Patients who permanently discontinue study treatment for other reasons than objective RECIST disease progression should be followed according to the study schedule similar to patients who are on study treatment.

All patients will be followed for survival until the end of the study. Patients who decline to return to the site for evaluations should be contacted by telephone if they agree.

7.3.2 Lost to follow-up

Patients will be considered lost to follow-up only if no contact has been established by the time the study is completed, such that there is insufficient information to determine the patient's status at that time. Investigators should document attempts to re-establish contact with patients.

In order to support key end points of PFS and OS analyses, the survival status of all patients in the full analysis and the safety analysis sets should be re-checked, this includes those patients who withdrew consent or are classified as "lost to follow-up". For patients lost to follow-up, site personnel should check hospital records, the patients' current physician, and a publicly available death registry (if available) to obtain survival status.

If a patient has actively withdrawn consent to the processing of their personal data, the survival status of the patient can be obtained by site personnel from publicly available death registries (if available) where it is possible to do so under applicable local laws to obtain a current survival status.

7.3.3 Withdrawal of consent

Patients are free to withdraw from the study at any time without prejudice to further treatment. Patients who withdraw consent for further participation in the study will not receive any further study treatment or further study observation, with the exception of follow-up for survival, which will continue until the end of the study unless the patient has expressly withdrawn their consent to survival follow-up. Note that the patient may be offered additional tests or tapering of treatment to withdraw safely.

A patient who withdraws consent may be asked about the reason(s) for withdrawal and the presence of any AE but does not have to give reasons for withdrawing. The Investigator will follow up AEs outside of the clinical study. If a patient withdraws consent, they will be specifically asked if they also withdraw consent to all further follow-up (e.g. survival contact phone calls).

7.4 End of trial

Patients will be enrolled until the target number of patients who have received three or more courses of chemoimmunotherapy in the control arm and the target number of patients who have received three or more courses of chemoimmunotherapy plus TRT in the experimental arm have been reached. Recruitment will stop earlier if:

- recommended by the Data and Safety Monitoring Committee
- recruitment of patients is so slow that it is not possible to answer the research questions within a reasonable timeframe. This will be decided by Sponsor after discussion with National Coordinating Investigators.
- new data show that eligible patients should be offered other and better treatment.
- new data show that participation puts patients at unreasonable risk and/or there are no reasons to believe that the patients benefit from participating in the trial.

8. Study therapy

8.1 Durvalumab

8.1.1 Durvalumab schedule

All patients will receive 1500 mg durvalumab IV on day 1 of each chemotherapy course regardless of delays of chemotherapy courses. Durvalumab is administered before carboplatin/etoposide.

After completion of chemotherapy, they will then receive durvalumab 1500 mg IV every 4 weeks until PD and need for other treatment, unacceptable toxicity or patients wish to discontinue.

If a patient's weight falls to 30 kg or below (≤30 kg) the patient should receive weight-based dosing equivalent to 20 mg/kg of durvalumab until the weight improves to >30 kg, at which point the patient should start receiving the fixed dosing of durvalumab 1500 mg.

8.1.2 Formulation/packaging/storage

Durvalumab will be supplied by AstraZeneca as a 500-mg vial concentrate for solution for infusion. The solution contains 50 mg/mL durvalumab, 26 mM histidine/histidine-hydrochloride, 275 mM trehalose dihydrate, and 0.02% weight/volume (w/v) polysorbate 80; it has a pH of 6.0 and density of 1.054 g/mL. The label-claim volume is 10.0 mL.

Durvalumab is a sterile, clear to opalescent, colorless to slightly yellow solution free from visible particles. Investigational product vials are stored at 2°C to 8°C (36°F to 46°F) and must not be frozen. Investigational product should be kept in original packaging until use to prevent prolonged light exposure.

8.1.3 Preparation of durvalumab doses for administration with an IV bag

The dose of durvalumab for administration must be prepared by the Investigator's or site's designated IP manager using aseptic technique. Please refer to local prescribing information for in-use storage conditions and times.

A dose of 1500 mg (for patients >30 kg in weight) will be administered using an IV bag containing 0.9% (w/v) saline or 5% (w/v) dextrose, with a final durvalumab concentration ranging from 1 to 15 mg/ml and delivered through an IV administration set with a 0.2- or 0.22- μ m filter. Add 30 mL (i.e. 1500 mg) of durvalumab to the IV bag. Mix the bag by gently inverting to ensure homogeneity of the dose in the bag.

If a patient's weight falls to \leq 30 kg weight-based dosing at 20 mg/kg will be administered using an IV bag size selected such that the final concentration is between 1 and 15 mg/mL.

Standard infusion time is 1 hour, however, if there are interruptions, the total infusion time must not exceed 8 hours at room temperature. Do not co-administer other drugs through the same infusion line.

The IV line will be flushed according to local practice to ensure that the full dose is administered. Infusion time does not include the final flush time.

If either preparation time or infusion time exceeds the time limits a new dose must be prepared from new vials. Durvalumab does not contain preservatives, and any unused portion must be discarded.

